8.2.4. AAV2/6 clearance in plasma, saliva, urine, stool, and semen

Presence and shedding of AAV2/6 vector DNA, by PCR in plasma, saliva, urine, stool and semen (males only) will be conducted over time from Baseline till Week 48. The level of vector genome from each type of sample will be summarized by visit. A corresponding listing and summary table will be provided.

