## **9.21 Vector Genome PCR**

Plasma, saliva, stool, and semen (males only) samples will be analyzed by PCR to determine clearance of SB-318 vector genomes. Each type of sample (plasma, saliva, urine, stool, semen) should be collected until 3 consecutive specimens of that sample type are reported as negative or undetectable for vector genome. Collection of semen samples may be waived for pediatric subjects (cohorts 4 through 7) at the discretion of the Principal Investigator. For details, refer to the Laboratory Manual.

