### 13.5 Secondary Endpoints

The following are secondary endpoints for this study:

- Change from Baseline in:
  - IDUA activity measured in blood.
  - Total GAG, DS GAG, and HS GAG levels (expressed as ratio to creatinine) measured in urine.
  - Monthly and annualized frequency and dose of Aldurazyme (or equivalent ERT).
- AAV2/6 clearance measured by vector genomes in plasma, saliva, urine, stool, and semen by PCR.

At each sampling time point, the actual value and the change from baseline for IDUA activity and GAG levels in urine will be summarized using descriptive statistics and plotted over time by treatment cohort.

For subjects who undergo ERT withdrawal, changes from pre- to post- ERT withdrawal in the frequency and dose of ERT infusions will be evaluated and summarized using monthly, quarterly, and annualized total dose and number of infusions. Duration of ERT withdrawal may also be analyzed.

AAV2/6 clearance measured by vector genomes in the different samples will be plotted over time by treatment cohort.

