- e. Liver panel will be performed twice a week for the first 20 weeks post-SB-318 infusion and may be remotely. Blood samples will be drawn 2-4 days apart when possible, except for the first week when it will be drawn on the Day 1 and Day 7 visits. Liver function tests will subsequently be conducted at all indicated study visits.
- f. For adult subjects (cohorts 1 through 3), the assay will be performed on blood or saliva samples. For post-transplant subjects, the assay will be performed on saliva samples only. For pediatric subjects (cohorts 4 through 7), saliva samples are preferred.
- g. For post-HSCT patients only.
- h. During Screening, samples for GAG testing in urine will be collected on 3 separate days, each collection occurring at least 7 days after the previous. All samples for GAG testing in the urine must be collected at least 7 days after ERT administration [+/- 1 day] but prior to the next ERT infusion.
- i. For IDUA/GAG testing in blood, samples must be obtained 7 days after ERT administration (+/- 1 day) and prior to the next ERT infusion. GAG and IDUA levels in blood will both be measured concurrently from the same blood sample.
- j. Each type of sample (plasma, saliva, urine, stool, semen) will be collected until 3 consecutive specimens of that sample type are reported as negative or undetectable for vector genome. Collection of semen samples may be waived for male pediatric subjects (cohorts 4 through 7) at the discretion of Principal Investigator.
- k. As permitted by subject's capacity. Neurocognitive abilities testing in pediatric subjects will be done by VABS-II and by WASI-II, WPPSI-IV, or BSID-III, as appropriate based on the Neurocognitive Abilities Assessment performed at Screening.
- l. Baseline MRI of brain and cervical spine may be obtained at Screening (together with MRI for liver) instead of at Baseline at the discretion of the Principal Investigator.
- m. Should prednisone or equivalent corticosteroid treatment be continued or repeated due to increased transaminase activity, the ACTH stimulation test will be repeated at the end of taper. Vital signs should be monitored and recorded every hour during the ACTH stimulation test.
- n. Unless contraindicated by a Principal Investigator or physician.
- o. May be waived for pediatric subjects (cohorts 4 through 7) at the discretion of the Principal Investigator to minimize required blood volumes.
- p. See [Appendix 3](#).

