3.4. Dose Modifications

No dose modifications are possible within an individual subject since this is a single infusion study.

4. General Statistical Considerations

Study days will be numbered relative to the date of SB-318 infusion. For assessments on or after the date of SB-318 infusion, the study day of events from SB-318 infusion is calculated as the date of event minus the date of infusion. For assessments prior to the date of SB-318 infusion, the study day of events from SB-318 infusion is calculated as the date of event minus the date of infusion. Thus, the study day of event before the date of the infusion will be negative number, and the study day of the date of infusion will be 0.

Baseline is defined as the last non-missing measurement prior to the SB-318 infusion. Where only date is available, the date of the collection must be prior to the date of SB-318 infusion. Where time is also available, the time of the collection must be prior to the time

of SB-318 infusion. For example, for vital signs parameters, measures that are taken at the latest time prior to the infusion will be defined as baseline values. Measurements that are obtained after infusion will be considered as post-baseline values. If the measurement of a variable is not made on a given subject prior to infusion, then that subject will be considered not to have a baseline value for that variable. Change from baseline is defined as post-baseline assessment minus baseline assessment.

Continuous data will be summarized using the following descriptive statistics: number of subjects (n), mean, standard deviation (SD), median, minimum and maximum, where appropriate. Categorical data will be summarized using the frequency count (n) and percentage (%) of subjects for each category, where appropriate.

Unless specified otherwise, all the summary tables will be presented by treatment cohort and overall, and all the collected data will be presented in the listings, and data displayed in the listings will be sorted by treatment cohort and subject identifier.

No imputation will be applied for missing data unless otherwise specified.

All analyses will be conducted using SAS® Version 9.3 or later. The Medical Dictionary for Regulatory Activities (MedDRA 23.0) will be used for coding adverse events.

Concomitant medication data will be coded using the World Health Organization (WHO) Drug Dictionary.

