Prog Notes: Post-baseline visits to be summarized include Weeks 4, 8, 12, 16, 20, 24, 28, 32, 36, 40, 44, 48, 52, Months 15, 18, 21, 24, 27, 30, 33, 36/EOS, or Early Termination Visit if applicable. Repeat for parameters in the following PARAMCD order: CREAT, MM1DR, MM1DU, MM1HR, and MM1HU.

Table 14.2.3
Change from Baseline in AAV2/6 Clearance
Safety Set

Parameter: AAV2/6-hIDUA (Copies/10 ul Plasma)

Visit	SB-318 1.00E+13 vg/kg (N=xx)		SB-318 5.00E+13 vg/kg (N=xx)		Total (N=xx)	
	Actual Value	Change From Baseline [1]	Actual Value	Change From Baseline [1]	Actual Value	Change From Baseline [1]
BASELINE						
n	xx		xx		xx	
MEAN (SD)	xx.x (xx.xx)		xx.x (xx.xx)		xx.x (xx.xx)	
MEDIAN	xx.x		xx.x		xx.x	
MIN, MAX	xx, xx		xx, xx		xx, xx	
VISIT X						
n	xx	xx	xx	xx	xx	xx
MEAN (SD)	xx.x (xx.xx)	xx.x (xx.xx)	xx.x (xx.xx)	xx.x (xx.xx)	xx.x (xx.xx)	xx.x (xx.xx)
MEDIAN	xx.x	xx.x	xx.x	xx.x	xx.x	xx.x
MIN, MAX	xx, xx	xx, xx	xx, xx	xx, xx	xx, xx	xx, xx

..
Note: Baseline is defined as last non-missing measurement prior to dosing.

[1]Change from baseline: post-baseline value - baseline value. For the change from baseline, only subjects with a value at both baseline visit and the specific post-baseline visit are included.

Source Data: Listing 16.2.9.6.1

<DIRECTORY PATH>PROGRAM NAME Executed: DDMMYYYY hh:mm

Prog Notes:

1. Please repeat for test AAV2/6-ZFN 47171 and other specimen (Saliva, Urine, Stool and Semen (Males Only)).
2. Post-baseline visit to be summarized include Day 7, Weeks 2, 4, 8, 12, 16, 20, 24, 36, 48.
3. Display visit Day 1 (12hr post-infusion) for Plasma only.

Table 14.2.4
Change from Baseline in Forced Vital Capacity (FVC)
Safety Set

Parameter: FVC (%)

Visit	SB-318 1.00E+13 vg/kg (N=xx)		SB-318 5.00E+13 vg/kg (N=xx)		Total (N=xx)	
	Actual Value	Change From Baseline [1]	Actual Value	Change From Baseline [1]	Actual Value	Change From Baseline [1]
BASELINE						
n	xx		xx		xx	
MEAN (SD)	xx.x (xx.xx)		xx.x (xx.xx)		xx.x (xx.xx)	
MEDIAN	xx.x		xx.x		xx.x	
MIN, MAX	xx, xx		xx, xx		xx, xx	
VISIT X						
n	xx	xx	xx	xx	xx	xx
MEAN (SD)	xx.x (xx.xx)	xx.x (xx.xx)	xx.x (xx.xx)	xx.x (xx.xx)	xx.x (xx.xx)	xx.x (xx.xx)
MEDIAN	xx.x	xx.x	xx.x	xx.x	xx.x	xx.x
MIN, MAX	xx, xx	xx, xx	xx, xx	xx, xx	xx, xx	xx, xx

...
Note: Baseline is defined as last non-missing measurement prior to dosing.

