Subject ID	Age (yrs) / Sex / Race	Visit	Collection Date (Day)	Category	Parameter	Result
XXXXXX	50/M/W	XXXXXXXX	DDMMYYYY (xx)	xxxxxx	xxxxxx	xx.x
		XXXXXXXXXX	DDMMYYYY (xx)	xxxxxx	xxxxxx	xx.x
		XXXXXXXXXX	DDMMYYYY (xx)	xxxxxx	xxxxxx	xx.x
XXXXXX	42/F/J	XXXXXXXX	DDMMYYYY (xx)	xxxxxx	xxxxxx	xx.x
		XXXXXXXXXX	DDMMYYYY (xx)	xxxxxx	xxxxxx	xx.x
		XXXXXXXXXX	DDMMYYYY (xx)	xxxxxx	xxxxxx	xx.x

Sex: M=Male, F=Female;

Race: W=White, BL=Black or African American, AS=Asian, AI=American Indian or Alaska Native, PI=Native Hawaiian or Other Pacific Islander, O=Other, NS=Not Specified

Day = date of event - date of infusion.

<DIRECTORY PATH>PROGRAM NAME Executed: DDMMYYYY hh:mm

Prog Note: Sort by Cohort, Subject ID, Collection Date, Test.

Listing 16.2.9.6.1
AAV2/6 Clearance
Enrolled Set

Cohort: SB-318 1.00E+13 vg/kg

Subject ID	Age (yrs) / Sex/		Collection Date (Day)	Test	Specimen Type	Result	Unit	Comments
	Race	Visit						
XXXXXX	50/M/W	XXXXXXXX/XXXXX	DDMMYYYY (XX)	AAV2/6- HIDUA AAV2/6- ZFN 47171	Plasma Saliva Stool Semen Urine Plasma Saliva	XXX.X XXX.X XXX.X XXX.X XXX.X XXX.X XXX.X	Copies/10 ul Plasma Copies/100ng Saliva DNA Copies/100ng XXXXXXXXX Stool DNA Copies/100ng Semen DNA Copies/250 ul Urine Copies/10 ul XXXXXXXXX Plasma Copies/100ng Saliva DNA	
					...			

Sex: M=Male, F=Female;

Race: W=White, BL=Black or African American, AS=Asian, AI=American Indian or Alaska Native, PI=Native Hawaiian or Other Pacific Islander, O=Other, NS=Not Specified

Day = date of event - date of infusion.

<DIRECTORY PATH>PROGRAM NAME Executed: DDMMYYYY hh:mm

Prog Note: Sort by Cohort, Subject ID, Collection Date, Test, Specimen Type. For Result, display the number of decimal places where Applicable exactly as they are in the data.

Listing 16.2.9.6.2
Immunogenicity Antibodies to AAV6 by Visit
Enrolled Set

Cohort: SB-318 1.00E+13 vg/kg

Subject ID	Age (yrs) / Sex / Race		Collection Date	Test	Specimen Type	Result	Interpretation	Units	Analysis Tiers		Comments
	Visit	(Day)							Tiers	Comments	
XXXXXX	50/M/W	XXXX	DDMMYYYY (XX)	Anti-AAV6_Ab_Screen	Serum	XXX.X	Potentially Positive	S/N (signal/noise)	1.35		
				Anti-AAV6_Ab_Confirmatory	Serum	XXX.X	Positive	%inhibition	17.2		
				Anti-AAV6_Ab_titer	Serum	XXX.X	Negative	titer	1.35	XXXXXXXXXX	

Sex: M=Male, F=Female;

Race: W=White, BL=Black or African American, AS=Asian, AI=American Indian or Alaska Native, PI=Native Hawaiian or Other Pacific Islander, O=Other, NS=Not Specified

Day = date of event - date of infusion.

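### AAV2/6 clearance is tabulated only as observed vector level by visit, so subjects confirmed clear can drop out of later rows and no table shows who cleared or when

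*SAP*

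**What the plan says.** Protocol 13.5 and SAP 3.2.2 make AAV2/6 clearance, measured by PCR in plasma, saliva, urine, stool and semen, a secondary endpoint.

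- **Sampling rule.** Protocol 9.21 states that each specimen type "should be collected until 3 consecutive specimens of that sample type are reported as negative or undetectable for vector genome". Appendix 1, footnote j, repeats the rule.
- **Schedule.** Protocol 6.6 to 6.8 place the PCR samples at Day 7 and at visits from Week 2 to Week 48, with an extra plasma sample on Day 1 (6.5). Protocol 6.9 (Months 15 to 36) and 6.10 (early termination) list none.
- **Planned analysis in the SAP.** SAP 8.2.4: "The level of vector genome from each type of sample will be summarized by visit", with one listing and one summary table.
- **Missing data.** SAP section 4: "No imputation will be applied for missing data unless otherwise specified". SAP 8.2.4 makes no exception.
- **Table shell.** Table 14.2.3 shows n, mean (SD), median, minimum and maximum of the actual value and of change from baseline, for two vector targets (hIDUA and ZFN 47171). Its note reads: "Post-baseline visit to be summarized include Day 7, Weeks 2, 4, 8, 12, 16, 20, 24, 36, 48". A Day 1 row is added for plasma.
- **Planned display in the protocol.** Protocol 13.5: "AAV2/6 clearance measured by vector genomes in the different samples will be plotted over time by treatment cohort".

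**The concern.** Whether a late value exists can depend on the result itself. Sampling of a specimen type may stop because the vector is gone, and the table uses only values that were observed. The late rows can then describe only the subjects not yet confirmed clear, and so make vector appear to persist longer or at higher levels than it does in the cohort as a whole.

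The table also does not answer the question its endpoint asks. A falling n could mean clearance, a missed sample, early termination, or transfer to the long-term follow-up study, which Protocol 6.9 allows case by case even before 12 months. Nothing in the table separates these. With planned cohorts of one or two subjects, a single absent subject halves or empties a row.

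**Working it through.** The plan states no figure for this endpoint, so there is none to reproduce. The check has four parts.

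**1. Effect on a late-row mean.** Take N subjects in a column, of whom c are confirmed clear and no longer sampled. Let S > 0 be the sum of the levels in those still sampled.

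- Displayed mean = S/(N − c)
- Mean with the cleared subjects kept at 0 = S/N
- Ratio = N/(N − c)

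| N | c | Ratio |
|---|---|---|
| 2 (planned Cohort 2) | 1 | 2/1 = 2.0 |
| 3 (Total column, 1 + 2) | 1 | 3/2 = 1.5 |
| 3 | 2 | 3/1 = 3.0 |
| 4 (cohort expanded by 2) | 1 | 4/3 = 1.33 |
| 4 | 2 | 4/2 = 2.0 |
| 4 | 3 | 4/1 = 4.0 |

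With N = 1 (Cohort 1) no inflation is possible. If every subject has cleared, the row is blank. Scoring a negative as 0 is an assumption, because the documents give no numeric value for an undetectable result. With a score L > 0 the comparator becomes (S + cL)/N, which is larger, so the ratios above are upper limits in that respect.

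**2. Rows affected.** For saliva, urine, stool and semen, Table 14.2.3 has 10 post-baseline rows: Day 7 and Weeks 2, 4, 8, 12, 16, 20, 24, 36 and 48. Counting three consecutive negatives along that schedule gives:

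| First negative | Third negative | Gap (weeks) | Later rows without the subject | Same, if the third result is reported one visit late |
|---|---|---|---|---|
| Day 7 | Week 4 | 3 | 7 | 6 |
| Week 2 | Week 8 | 6 | 6 | 5 |
| Week 4 | Week 12 | 8 | 5 | 4 |
| Week 8 | Week 16 | 8 | 4 | 3 |
| Week 12 | Week 20 | 8 | 3 | 2 |
| Week 16 | Week 24 | 8 | 2 | 1 |
| Week 20 | Week 36 | 16 | 1 | 0 |
| Week 24 | Week 48 | 24 | 0 | 0 |

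The last column matters because the protocol's trigger is the reported result, and no turnaround time is given. The gap column shows that any time to clearance differs by 3 to 24 weeks according to whether it is dated at the first or the third negative, so the SAP would have to say which.

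**3. End of scheduled sampling.** A subject still positive at Week 24 has only Weeks 36 and 48 left. That is two samples where three are required, so clearance cannot be confirmed on the scheduled visits. Protocol 9.21 gives no end date, while Protocol 6.8 and SAP 8.2.4 end at Week 48.

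**4. Protocol against SAP.** Protocol 13.5 plans a plot of clearance over time by cohort. SAP 8.2.4 mentions a listing and a table only. The shells' table of contents lists tables and listings and no figure. SAP section 11 records one change, the dropped summary of ERT dose. The plot has therefore been removed without being recorded.

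**The case against.** The best case for the plan has four parts.

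- **No clearance count was promised.** The protocol defines the endpoint through vector genomes, and three negatives is a sampling rule. This is right: a count is an addition, not a missing planned analysis. The rule is not foreign to the trial, though; it also sets how long barrier contraception and pregnancy testing continue (Protocol 4.1 and 9.11).
- **The data are all shown.** Listing 16.2.9.6.1 gives every result by subject, date, target and specimen, and Listing 16.2.1.1 gives the completion or termination date with the reason for early termination. With so few subjects, clearance can be worked out by hand. This stands and limits the severity. The clearance listing carries no clearance flag or date, however, so each reader would have to choose a definition.
- **The ratios rest on conditions.** Sites must stop sampling, results must be back in time, subjects in one column must differ, and negatives must be scored as 0. The displayed mean is also correct for the n it shows. All of this is true. At planned sizes the only within-cohort ratio for the two displayed doses is 2.0, in a row labelled n = 1.
- **The missing plot is wider than this endpoint.** Protocol 13.5 also plots IDUA activity and urine GAG, and SAP 8.2 drops those plots too. That is correct, and one entry in SAP section 11 could cover all three. It does not excuse the omission here.

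**Conclusion.** The concern holds. Followed as written, the plan can remove confirmed-clear subjects from the later rows of its own clearance table, and no table reports who cleared or when. Where the effect arises, a late-row mean is 2.0 times the cleared-at-0 value for one of two subjects, 1.5 or 3.0 times in a Total column of three, and up to 4.0 times in an expanded cohort of four. Up to 7 of 10 rows can lack an early clearer.

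This rests on sites stopping as the rule allows, on at least one subject in the column staying positive, and on negatives counted as 0. How often that happens cannot be known from the documents. Because the study is small and descriptive with full listings, this is a minor to moderate reporting improvement that should be made. The unrecorded loss of the plot, and the mismatch between Protocol 9.21 and the Week 48 end of sampling, stand whether or not any site stops early.

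**What to change.** In SAP 8.2.4:

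1. Define confirmed clearance per specimen type as three consecutive post-infusion samples negative or undetectable for every vector target tested. Date it at the first of the three and count it as confirmed from the third.
2. Add to Table 14.2.3, by visit, cohort and specimen type: n/N confirmed clear, n still sampled and not confirmed, and n off study or missing.
3. Give each subject's time to clearance, or state that it was not confirmed by the last sample. Report specimen types that were never positive separately.
4. Keep the level summaries on observed values, with a footnote that confirmed-clear subjects may no longer be sampled. If a carried-forward negative is shown, make it a labelled supplementary row, limited to unsampled visits after confirmation while the subject is on study, and never in place of an observed result. That row assumes that confirmed clearance persists.
5. Restore the plot from Protocol 13.5 or list its removal in SAP section 11.

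The cost is SAP wording, one revised table shell, and a figure or one line in section 11, with no new samples. Separately, Protocol 9.21 must be reconciled with the Week 48 end of sampling in Protocol 6.8 and SAP 8.2.4, which may need a protocol clarification or amendment.

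### AAV2/6 clearance is summarised only as vector level among subjects still being sampled; no summary output says how many cleared or when

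*SAP*

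**What the plan says.** Protocol 13.5 and SAP 3.2.2 list AAV2/6 clearance, measured by PCR in plasma, saliva, urine, stool and semen, as a secondary endpoint. Under Protocol 9.21 and Appendix 1 footnote j, each specimen type is collected only until three successive specimens are negative or undetectable.

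SAP 8.2.4 says that testing "will be conducted over time from Baseline till Week 48" and that "The level of vector genome from each type of sample will be summarized by visit". It provides one listing and one summary table.

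The shell for Table 14.2.3 gives n, mean (SD), median, minimum and maximum of copies and of change in copies, in columns for 1.00E+13, 5.00E+13 and Total. Its second programming note reads "Post-baseline visit to be summarized include Day 7, Weeks 2, 4, 8, 12, 16, 20, 24, 36, 48", with Day 1 added for plasma. Its footnote on the change column says that "only subjects with a value at both baseline visit and the specific post-baseline visit are included". Its first programming note repeats the table for a second PCR test (ZFN 47171) and for the other specimens. SAP 4 adds: "No imputation will be applied for missing data unless otherwise specified".

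Subject-level results are in Listing 16.2.9.6.1, whose note reads "Sort by Cohort, Subject ID, Collection Date, Test, Specimen Type".

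Protocol 13.5 also planned a figure: "AAV2/6 clearance measured by vector genomes in the different samples will be plotted over time by treatment cohort". SAP 8.2.4 has no figure, the shells' table of contents lists none, and SAP 11 records only the dropped summary of ERT dose.

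**The concern.** Sampling of a specimen stops because of its own result. A subject who clears therefore leaves the by-visit table instead of staying in it as a negative. Once the first subject stops, the later-visit mean, median and range describe a group selected for not yet having completed three negatives. The effect falls mainly on the Total column, where several subjects are pooled.

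The printed n falls, but the table does not say whether the cause is clearance, a missed sample or withdrawal. No summary output counts the subjects who cleared or gives the time this took, which is what a reader of a clearance endpoint wants to know. Read alone, the table could suggest persistent or rising vector when most subjects have cleared.

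**Working it through.** **Inputs.** The documents give no clearance rate, clearance time or precision for this endpoint, so there is no stated figure to reproduce.

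- Post-infusion visits (Table 14.2.3, second programming note; Protocol 6.6 to 6.8): Day 7 and Weeks 2, 4, 8, 12, 16, 20, 24, 36 and 48, which is 10. Plasma also has Day 1.
- Stop rule: three consecutive negatives (Protocol 9.21; footnote j).
- Planned subjects (SAP 3.1): adults 1 + 2 + 2 = 5; the two doses printed in the shells 1 + 2 = 3.

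**When a subject leaves the table.** If a specimen is lastingly negative from a given visit, the last sample is two visits later. This assumes that results are back before the next visit; slower reporting means later stopping and less selection.

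- Negative from Day 7: last sample Week 4, 3 of 10 visits.
- Negative from Week 4: last sample Week 12, 5 of 10 visits.
- Negative from Week 16: last sample Week 24, 8 of 10 visits.

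**Size of the selection.** Let N be the dosed subjects due the specimen and n those still sampled. If negativity lasts and a negative counts as 0, subjects who have stopped add nothing to the sum. Then

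mean among sampled = mean over all × N / n,

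and the same holds for the proportion positive.

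**Illustration (assumed levels: 100 before clearing, 0 after).** Take the 5 planned adults. Four have lasting first negatives at Day 7, Week 2, Week 4 and Week 8, so their last samples are at Weeks 4, 8, 12 and 16. The fifth never clears.

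| Visit | n | Mean in table | Mean with cleared kept as 0 |
|---|---|---|---|
| Week 4 | 5 | (0+0+0+100+100)/5 = 40 | 200/5 = 40 |
| Week 8 | 4 | (0+0+0+100)/4 = 25 | 100/5 = 20 |
| Week 12 | 3 | (0+0+100)/3 = 33.3 | 20 |
| Week 16 | 2 | (0+100)/2 = 50 | 20 |
| Week 20 on | 1 | 100/1 = 100 | 20 |

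The formula agrees: 20 × 5/4 = 25, 20 × 5/3 = 33.3, 20 × 5/2 = 50, 20 × 5/1 = 100. From Week 8 the truth is 4 of 5 negative, and no subject's level ever rises.

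**Range.**

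- Nobody stops before Week 48: N/n = 1, so there is no distortion.
- All clear together: every later sampled value is 0, so there is none either.
- Only the 3 subjects planned at the shells' two doses: minimum, median and maximum show every value in the Total column. What is missing is the count cleared and the reason n fell.

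**Work needed to recover clearance by hand.** The listing carries 2 PCR tests, so a male has 2 × 5 = 10 series and a female 2 × 4 = 8. Neither document says whether both tests must be negative, so two readers could date clearance differently from the same listing.

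**The case against.** The strongest reply is that the endpoint is worded as clearance measured by vector genomes, and vector level by visit reports that. Three negatives is a rule for sampling and contraception, not a stated endpoint definition. The study is descriptive, with no hypothesis tests and one or two planned subjects per cohort, for which a listing is an adequate display. The reason for a falling n can be pieced together from the PCR listing, the disposition table and listing, and the deviations listing. The five-adult illustration also includes a dose for which the shells have no column.

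Much of this stands and keeps the point small. It does not supply a summary of who cleared. A maximum at the negative level shows that everyone sampled was negative and says nothing about those no longer sampled. The three-negative rule is also the only operational rule the documents offer.

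Three stronger readings are tempting, and the documents do not support them.

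- A reader might infer that later visits contain only positive subjects. They contain subjects who have not completed three negatives. In the illustration, 3 of 4 are at zero at Week 8, 2 of 3 at Week 12 and 1 of 2 at Week 16.
- A reader might infer that the plot was dropped for clearance in particular. SAP 8.2 also omits the plots that Protocol 13.5 planned for IDUA activity and urine GAG, so this is a general omission. A plot of the same observed values would still lack a count.
- A reader might infer that sampling must be extended by amendment, because a specimen still positive at Week 24 has only Weeks 36 and 48 left. Protocol 9.21 gives no end date, but it can be read as early stopping within the visits listed in 6.8, and 6.9 and 6.10 list no PCR. The comparable pregnancy-test rule in 9.11 is also undated in the text and is capped at Week 48 by its Appendix 1 footnote. Barrier contraception continues until three negatives, so the rule fails safe. The Laboratory Manual and the long-term follow-up protocol are not among the documents.

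**Conclusion.** The point holds as a minor reporting gap. Followed as written, the SAP produces later-visit statistics selected on the outcome, and no summary of number cleared or time to clearance for a named secondary endpoint. No data are lost, since the listing holds every result, and no safety consequence is shown.

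In the assumed five-adult example the Total mean reaches 100 against 20 for all subjects. That size rests on assumed levels and clearance times, lasting negativity and prompt results. The number of subjects affected is unknown and may be zero.

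**What to change.** In SAP 8.2.4 and Table 14.2.3, add the following for each specimen type and cohort. The denominator is all dosed subjects who are due that specimen (for semen, males only).

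- The number with three consecutive negatives.
- The time from infusion to the first of those three.
- The number not cleared at last sample.

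State whether a negative requires both PCR tests (hIDUA and ZFN 47171). Either restore the Protocol 13.5 plot or record its removal in SAP 11, and treat the IDUA and urine GAG plots in the same way.

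The cost is one definition, three rows per specimen type and either figures or a line in SAP 11, all from data already collected. No extra sampling and no protocol amendment are needed.
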